CSF circulation. CSF, a clear colorless fluid secreted by the choroid plexuses, moves by bulk flow (*macrocirculation*) around the central nervous system (CNS), and ensures the health of the CNS⁶. Impaired CSF circulation can comprise the normal physiological functions of the CNS, which then may contribute to CNS diseases including neurodegenerative conditions⁷. Furthermore, CSF circulation plays a key role in maintaining glymphatic transportation of CSF (*microcirculation*). Recent research efforts^{8,9} have defined a "*glymphatic function*", a brain-wide clearance mechanism facilitates the clearance of solutes and metabolic wastes from the brain interstitium. Sleep and arousal state are critical regulators of glymphatic function, since CSF tracer influx and interstitial solute clearance are increased during both sleep and anesthesia compared to the wakefulness¹, which is associated with slowed amyloid beta clearance and more rapid amyloid plaque deposition². The impairment of glymphatic function underlies the development of CNS diseases in the aging brain remains unknown, so it is critical to better understand the complete mechanisms supporting CSF circulation in the human CNS by i) developing non-invasive approaches to measure CSF circulation, and ii) potentially identifying therapies that can regulate and enhance CSF circulation. For this aim, we recently developed novel non-invasive imaging approaches to quantify CSF dynamics ¹² and we aim to study YB as a potential therapy for regulating and enhancing CSF circulation.

4) Study Design

This study is the K99 phase of the NIH-NCCIH K99/R00 study K99AT010158.

Protocol. The study protocol consists of 20 healthy young subjects undergoing an 8-week intervention (10 subjects in arm 1 and 10 subjects in the active control arm 2), and outcome measures within a 2-week period of pre-and post-intervention. We will test the hypothesis that the yogic breathwork practice with sophisticated breathing practices, compared to active control will enable participants to sustain slow and rhythmical breathing patterns and create larger modulations in their CSF dynamics.

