Post-acquisition, each data set will be examined for quality and completeness by the trained study team.

CSF flow:

- CSF flow data analysis will be performed using a semiautomated pulsatility-based segmentation procedure. The velocity waveform will be averaged over the highly correlated ROI pixels. The maximum and minimum peak values of the averaged CSF flow velocities will then be used for analysis (see details below *Statistical Analysis*).
- The respiration frequency band and the cardiac frequency band will be defined based on the two main distinct peak amplitudes of the frequency spectrum of the averaged CSF velocity waveforms measured with RT-PCMRI.
- The relative contribution of the respiration versus cardiac component of the CSF velocity waveforms will then be quantified by defining a power ratio between respiratory component and the cardiac component.

Respiration and ECG data:

- The pulse ox and respiration data collected during the RT-PCMRI acquisitions will be filtered using a 4th order Butterworth to extract only the respiration and only cardiac component.

Wearable device:

- Respiration data from wearable device collected during the 8-week intervention will be analyzed for the respiration rate and peak-to-peak respiration intervals. If collected, sleep data measured with wearable device will be analyzed to measure the influence of intervention on participants' long-term

sleep patterns objectively.

Self-report questionnaires:

- Response to self-report questionnaires will be analyzed for the statistical analysis to compare the changes in subject's quality of life, sleep, and existing stress levels.

Statistical Analysis

- The major dependent variables will be i) CSF flow metrics maximum and minimum (values of average CSF velocities; relative ratio of respiration vs. cardiac component of the CSF velocity; ratio of the maximum CSF velocity during breathing practices to the average of peak CSF velocities at baseline during natural breathing, ii) respiration rate and peak-to-peak respiration intervals and iii) self-reported questionnaire results. The effects of the interventions on these variables will be tested in a multivariate analysis of variance with repeated measures to compare pre- and post-intervention. An alpha value of 0.05 will be used for statistical significance.

9) Privacy, Confidentiality and Data Security

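### The hypothesis is larger CSF modulations, but peak-to-peak CSF velocity is never defined, so a significant maximum/minimum result would not by itself show a wider swing

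*Combined protocol and SAP*

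**What the plan says.** Section 2 (Objectives) and section 4 (Study Design) state the same hypothesis, that the practice will "enable participants to sustain slow and rhythmical breathing patterns and create larger modulations in their CSF dynamics". Section 4 adds that the comparison is with the active control.

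Section 8 (Data Analysis, CSF flow) summarises the ROI-averaged waveform by its two extremes: "The maximum and minimum peak values of the averaged CSF flow velocities will then be used for analysis".

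The Statistical Analysis part of section 8 then lists the CSF variables:
- The two extremes come first: "The major dependent variables will be i) CSF flow metrics maximum and minimum (values of average CSF velocities".
- Next is a relative measure, the power in the respiratory band set against that in the cardiac band.
- The last one sets the practice against natural breathing and uses the upper peak only: "ratio of the maximum CSF velocity during breathing practices to the average of peak CSF velocities at baseline during natural breathing".

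These variables, together with the respiration measures and the questionnaires, "will be tested in a multivariate analysis of variance with repeated measures to compare pre- and post-intervention". The only decision rule is "An alpha value of 0.05 will be used for statistical significance". No contrast between maximum and minimum is named, no CSF variable is singled out as primary, and no arm-by-time term is written out. Section 8 applies the term peak-to-peak to respiration intervals only, not to CSF velocity.

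**The concern.** A larger modulation of a velocity waveform is most directly read as a wider swing between its highest and lowest values. The plan extracts both values but never subtracts one from the other.

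A MANOVA on maximum and minimum asks whether the pair has changed in any direction. Maximum up and minimum down is a wider swing. Both up by the same amount is a shift in mean velocity, with the swing unchanged. The test does not tell these apart. A significant result could thus be reported as support for "create larger modulations in their CSF dynamics" when the waveform had moved and not widened.

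The two ratios do not close the gap. The respiratory-to-cardiac power ratio is immune to a constant offset, but if both components grow by the same factor k it becomes kR/kC = R/C and does not move. The practice-to-natural ratio takes only the maximum in its numerator and is not shift-proof: an offset c turns M/B into (M + c)/(B + c).

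**Working it through.** The documents give no power, SD, effect size or correlation, so there is no figure to reproduce. The check illustrates how a joint test and a swing test behave.

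**From the documents:** n = 10 per arm (section 4), with up to 13 per arm allowed for loss (section 5a); alpha 0.05 (section 8).

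**Assumed:** equal SD of the pre-to-post change in maximum and minimum (1 unit); arm differences d_max and d_min in those SDs; correlation rho between the two changes, from -0.9 to 0.5.

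**Formulas.** With two time points, the arm-by-time MANOVA test is a Hotelling test on the changes.
- Joint test of (maximum, minimum): F with 2 and 2n - 3 = 17 df; noncentrality (n/2) D², where D² = (d_max² - 2 rho d_max d_min + d_min²)/(1 - rho²).
- Swing test (maximum minus minimum): F with 1 and 2n - 2 = 18 df; noncentrality (n/2)(d_max - d_min)²/[2(1 - rho)].

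**Worked case, rho = 0.**
- Pure shift (+1, +1): D² = 2, joint noncentrality 5 × 2 = 10, rejection 74%. Swing noncentrality 0, rejection 5%.
- Symmetric widening (+1, -1): D² = 2, joint noncentrality 10, power 74%. Swing noncentrality 5 × 4/2 = 10, power 85%. The signal is the same; the joint test spends one more degree of freedom.
- Maximum only (+1, 0): D² = 1, joint noncentrality 5, power 43%. Swing noncentrality 5 × 1/2 = 2.5, power 32%.

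**Rejection probability, 10 per arm, joint / swing:**

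| Arm difference (max, min) | rho -0.9 | rho -0.5 | rho 0 | rho 0.5 |
|---|---|---|---|---|
| Pure shift (+1, +1) | 100% / 5% | 96% / 5% | 74% / 5% | 55% / 5% |
| Symmetric widening (+1, -1) | 45% / 58% | 55% / 69% | 74% / 85% | 96% / 99% |
| Minimum moves half as far (+1, -0.5) | 70% / 37% | 43% / 45% | 52% / 61% | 80% / 89% |
| Maximum only (+1, 0) | 99% / 19% | 55% / 23% | 43% / 32% | 55% / 56% |

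Reading the rows:
- The shift row is the interpretability problem. It holds at every rho: the swing test stays at 5% and the joint test does not.
- For symmetric widening the swing gains about 11 to 13 points at rho from -0.9 to 0, and about 2.5 at rho = 0.5.
- When the minimum moves half as far, the order reverses just below rho = -0.5: at rho = -0.6 the joint test has 43.8% and the swing 42.7%.
- When only the maximum moves, the swing loses at rho of zero or below: by 11 points at rho = 0 and by 32 at rho = -0.5.

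At 13 per arm the pattern is the same. With rho = 0, symmetric widening gives 87% joint and 93% swing; maximum only gives 56% and 41%.

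**The case against.** The strongest case against has five parts.

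1. *A reader might infer that the peaks are tested in separate univariate tests.* The documents do not say so. Section 8 names a multivariate analysis, and its alternative includes the difference. This stands; the point is only that the joint test does not isolate the difference or its direction.

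2. *A velocity offset between scans that is common to both arms cancels in the randomised comparison.* This stands. The pure-shift row needs a shift that differs by arm, and nothing in the documents suggests that one is likely. A common offset does harm only if the pre/post effect is read within arm. That reading remains open, because section 8 speaks of comparing pre with post and writes out no arm-by-time term.

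3. *Modulation is already measured.* Largely fair. The documents do not define modulation as maximum minus minimum, and the respiratory-to-cardiac power ratio is a modulation measure that an offset cannot move. It would be wrong to infer that the plan leaves modulation unmeasured. What is missing is its absolute size.

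4. *The two-variable test is not the planned one.* This stands. The planned MANOVA also takes in respiration measures and questionnaires, so the percentages above are not the plan's own rejection rates.

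5. *Maximum and minimum are both kept, so a reader can see whether the waveform widened or shifted.* This limits the harm. It does not supply a pre-specified test of the swing or a rule for what counts as widening.

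**Conclusion.** The point holds as one of interpretability. The hypothesis concerns larger modulations, the direct absolute measure of them is not defined, and a significant maximum/minimum result does not by itself establish a wider swing. Under an assumed same-direction arm difference of 1 SD in both peaks, a two-variable joint test would reject 55% to 96% of the time for rho from 0.5 to -0.5 with no change in swing.

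A reader might also infer that the planned analysis generally has less power for a real widening than a test of the swing. The documents do not support that. The advantage depends on rho, the SDs and the shape of the effect, none of which is given, and it reverses when mainly one peak moves and rho is zero or negative. The case for change rests on tying the result to the hypothesis, not on power. This is a cheap improvement to make before analysis and not a flaw that invalidates the design.

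**What to change.** In section 8:

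- Add peak-to-peak CSF velocity (maximum minus minimum of the averaged ROI waveform, for each breathing condition and visit) as a pre-specified CSF variable.
- Compare its pre-to-post change between arms.
- State that a maximum/minimum result will be read as a wider swing only if peak-to-peak velocity increases.
- Keep maximum, minimum and the two ratios as planned variables; the two peaks then show which direction of flow changed.
- Do not enter maximum, minimum and their difference in the same MANOVA. They are linearly dependent, so the error matrix would be singular. Test the difference in its own model.

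The cost is one variable derived from values already extracted and a few sentences of text. The downsides are one extra test and lower power for the swing if only one peak moves (for example 32% against 43% at rho = 0). Retaining maximum and minimum covers that case.

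### The respiratory and cardiac bands are read from the CSF spectrum being measured, so a weak respiratory peak could be mislabelled; the recorded respiration and pulse-ox traces should set them

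*Combined protocol and SAP*

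**What the plan says.** Under CSF flow in section 8, both frequency bands are to be defined from the "two main distinct peak amplitudes of the frequency spectrum of the averaged CSF velocity waveforms measured with RT-PCMRI". The relative contribution of the two sources is then "quantified by defining a power ratio between respiratory component and the cardiac component". The Statistical Analysis paragraph lists the "relative ratio of respiration vs. cardiac component of the CSF velocity" among the major dependent variables.

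The next heading, Respiration and ECG data, shows that independent signals exist: "The pulse ox and respiration data collected during the RT-PCMRI acquisitions will be filtered using a 4th order Butterworth", to separate the respiratory and cardiac components. No sentence says that these traces set or check the bands used on the CSF spectrum.

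The plan states no frequency limits for either band, no band width, no treatment of harmonics, and no rule for a scan in which no respiratory peak stands out.

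**The concern.** A pulsatile waveform usually has power at multiples of the heart rate as well as at the heart rate itself. If respiratory modulation of CSF velocity is weak in a scan, its peak may be lower than the second cardiac harmonic. The two main peaks are then the cardiac fundamental and its harmonic. Read literally, the lower of these becomes respiration and the higher becomes cardiac, and a scan with little respiratory power is recorded as dominated by respiration.

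The hypothesis in section 4 is that practice will "create larger modulations in their CSF dynamics". A measurement error that depends on the size of that modulation is worse than random noise, and with 10 subjects per arm a single mislabelled scan can dominate an arm mean.

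**Working it through.** The plan states no figure to reproduce, so the check is algebra followed by simulation.

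**Inputs.** From the documents: the peak-based band definition, the power ratio built on it, and 10 subjects per arm. Everything about the signal is assumed: cardiac fundamental amplitude 1 at 1.1 Hz, second harmonic amplitude h at 2.2 Hz, respiratory amplitude a at 0.25 Hz, 60 s sampled at 8 Hz, noise SD 0.3, half-band 0.15 Hz.

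**Algebra.** Power is proportional to squared amplitude.

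- Correct labels: ratio = a²/1² = a².
- If a < h and the two tallest peaks are taken, with the lower called respiration: ratio = 1²/h² = 1/h².
- h = 0.3: 1/0.09 = 11.1, where the true ratio is below 0.3² = 0.09.
- h = 0.5: 1/0.25 = 4.0, where the true ratio is below 0.5² = 0.25.

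**Simulation.** 500 runs per setting, with 3% variation in both rates within the scan. The peak rule takes the two largest separated peaks and calls the lower one respiration. The reference method centres the bands on the known frequencies.

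| h | a | True a² | Mislabelled | Median ratio, peak rule | Median ratio, reference bands |
|---|---|---|---|---|---|
| 0.3 | 0.1 | 0.01 | 100% | 10.19 | 0.022 |
| 0.3 | 0.2 | 0.04 | 36% | 0.07 | 0.053 |
| 0.3 | 0.3 | 0.09 | 1% | 0.10 | 0.102 |
| 0.3 | 0.4 | 0.16 | 0% | 0.17 | 0.172 |
| 0.5 | 0.1 | 0.01 | 100% | 3.99 | 0.022 |
| 0.5 | 0.2 | 0.04 | 100% | 3.97 | 0.053 |
| 0.5 | 0.3 | 0.09 | 56% | 3.38 | 0.103 |
| 0.5 | 0.4 | 0.16 | 6% | 0.17 | 0.168 |
| 0.5 | 0.6 | 0.36 | 0% | 0.37 | 0.368 |

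Reference bands stay close to a² throughout, apart from a small noise contribution at the lowest amplitudes. Where respiration is clearly the larger peak, the two methods agree. In a similar simulation with h = 0.1, the rule failed in 5% of scans at a = 0.15 and in none at a = 0.25 or above.

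**Sensitivity to rate variation.** At h = 0.3 and a = 0.25, separate runs gave 86% and 94% mislabelled with perfectly steady rates, and 14% or less with 3% to 6% variation. The reason is that 3% variation moves the harmonic by 0.03 × 2.2 = 0.066 Hz but the respiratory line by only 0.03 × 0.25 = 0.0075 Hz. The harmonic is smeared and its peak falls.

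**Weight of one scan.** Take h = 0.3 and a = 0.25, so the true ratio is 0.0625. One mislabelled scan among ten shifts that arm's mean at that visit by (11.1 − 0.0625)/10 = 1.10, many times the value being estimated.

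**The case against.** The strongest reply is that the simulated rule is cruder than the plan's. The plan names a respiratory and a cardiac band and speaks of main, distinct peaks. It does not say to rank peaks blindly and call the lower one respiration. In the failure case the supposed respiratory peak lies at 1.1 Hz, or 66 breaths per minute, which is implausible in a resting adult. In simulation, 98% to 100% of mislabelled scans had that peak above 0.6 Hz (36 per minute), and requiring the respiratory peak to lie below 0.6 Hz brought the ratios back to the reference value. Section 8 also has trained staff examine each data set for quality and completeness. This stands as a reason to expect few uncaught errors. It does not close the gap: no plausibility check is written, and the quality review is not said to cover band labels. Further detail may lie in the imaging-method paper that the protocol cites, but the plan does not say that its rules apply here.

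Two stronger readings are tempting, and the documents support neither.

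- A reader might infer that a large, known share of scans will be wrong. The documents give no amplitudes, heart or breathing rates, scan duration or spectra, and the simulated rates depend heavily on those choices.
- A reader might infer that pre-intervention scans are the weakly modulated ones, so that the pre-to-post change is biased in a known direction. Section 6 (First imaging visit) has subjects instructed in and performing the breathing techniques at the first scan, and the second imaging visit repeats the procedures. Natural breathing is mentioned only in the denominator of a different metric, the "average of peak CSF velocities at baseline during natural breathing", which uses no frequency bands. No sentence says which breathing condition supplies the power ratio.

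**Conclusion.** The point holds as a conditional one. The plan takes its bands from the signal it is measuring, with no frequency limits or harmonic rule, and a literal application can turn a small ratio into one well above 1 (about 4 to 11 for harmonics of 0.5 to 0.3) when respiration is weaker than a cardiac harmonic. This rests on assumed signal values and on labelling the lower of the two peaks as respiration. Frequency of occurrence is unknown, with simulated rates from 0% to 100%. Neither a failure rate for this trial nor a direction of bias is established. What remains is a labelling rule left unwritten for a major dependent variable, when a better reference signal is already collected. It is a free improvement, not a demonstrated error.

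**What to change.** Amend the CSF flow paragraph of section 8 as follows.

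1. For each acquisition, centre the respiratory band on the fundamental of the concurrently recorded respiration trace and the cardiac band on the fundamental of the concurrent pulse-ox trace.
2. State one band-width rule before analysis, and apply it to both arms and both visits. It should keep the two bands from overlapping at the breathing rates expected.
3. Integrate CSF spectral power within those bands to form the ratio.
4. Where the CSF spectrum shows no visible respiratory peak, report the power in the respiratory band as low. Do not substitute another peak.

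The cost is a few sentences and a few lines of code. The traces are already recorded and filtered, so no new data, visits or participant burden are needed. Where the present rule works, the results will hardly change.

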Quantifying the Influence of Yogic Breathwork on Cerebrospinal Fluid Circulation

Unique Protocol Identification Number: STUDY00019281

National Clinical Trial (NCT) Identified Number: NCT03858309

Principal Investigator: [name]

Sponsor: Oregon Health & Science University

Grant Title: Quantifying the Influence of Yogic Breathwork on Cerebrospinal Fluid Circulation

Grant Number: K99AT010158

Funded by: NCCIH

November 11 2019

Principal Investigator or Clinical Site Investigator:

Name: [name]
Title: Senior Research Associate

Investigator Contact Information:

Affiliation: Oregon Health & Science University
Address: [name]
[contact]
Email: [contact]

1) Protocol Title

Quantifying the Influence of Yogic Breathwork on Cerebrospinal Fluid Circulation

2) Objectives

The purpose of this protocol is to determine the influence of an 8-week yogic breathwork intervention on cerebrospinal fluid (CSF) dynamics among healthy subjects using a non-invasive magnetic imaging (MRI) technique. We will examine this aim by studying the changes in each subject's pre- and post-intervention CSF dynamics using the non-invasive RT-PCMRI technique during two MRI scans (one before and one after the 8-week intervention). This aim will test the hypothesis that a regular yogic breathwork practice will enable participants to sustain slow and rhythmical breathing patterns and create larger modulations in their CSF dynamics.

3) Background

Yogic breathwork (YB) is an appealing mind-body therapy for healthcare management purposes because it is a low-risk and low-cost practice that can be easily learned and performed without any additional equipment. It is important to understand the mechanisms for the benefits of YB practices. Based on our preliminary results, we believe that another - less explored- potential mechanism for the positive effects of YB can be its direct influence on cerebrospinal fluid (CSF) circulation, which to date has not yet been quantified due to lack of non-invasive methodology.

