We plan to recruit 20 healthy subjects (18-65 years; 10 for each of the two groups) from the Portland community through IRB approved flyers posted around the OHSU campus and the city, and advertised in local media. While we do not expect that any participants will voluntarily drop from the study, unavoidable circumstances may arise and we expect to retain enough participants to collect sufficient data on intervention development, decisions on the appropriateness of our instruments, and burden to participants. In order to assure we have sufficient qualitative and quantitative data for this proposed study and any potential lost-to-follow up, we may recruit 13 people for each arm.

b) Inclusion and Exclusion Criteria

Inclusion criteria: 18-65 years of age, able to provide their consent to be in the study, available and able to participate in study activities, who can lie in supine, able to walk 15 feet, who have no prior/current regular mind-body practice inducing breath awareness or training such as yoga, meditation, Ta-Chi, Qi-Gong; a compatible device for physiological data trackers.

Exclusion criteria: inability to provide informed consent, MRI contraindications, need for muscle relaxants or anti-anxiety drugs in order to tolerate MRI, history of neurological disorders, head trauma with loss of consciousness, craniospinal disorders, spinal injury, sleep disorders, allergic or respiratory disorders, major or uncontrolled psychiatric illness or major depression, lung and heart problems, any condition requiring the use of medication that acts on the brain like stimulants, sedatives current substance abuse issues, pregnancy or nursing.

Optimization Scans:

Inclusion criteria: 18-65 years of age, able to provide their consent to be in the study, available and able to participate in 1-hour MRI scan, who can lie in supine, able to walk 15 feet.

Exclusion criteria: inability to provide informed consent, MRI contraindications, need for muscle relaxants or anti-anxiety drugs in order to tolerate MRI.

c) Vulnerable Populations

This study (K99 or R00 phase) will not include any vulnerable populations. We will not collect any information about subjects' status as prisoners, and will actively exclude pregnant women, children, neonates, and adults lacking capacity to provide informed consent.

d) Setting

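### Does dividing a single maximum by an average of peaks make the practice-to-natural CSF ratio unfit for the planned comparison?

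*Combined protocol and SAP*

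**What the plan says.** Section 8, Statistical Analysis, lists three CSF flow metrics: the maximum and minimum velocities, a respiratory-to-cardiac ratio, and the "ratio of the maximum CSF velocity during breathing practices to the average of peak CSF velocities at baseline during natural breathing". None is named as primary. The test is a "multivariate analysis of variance with repeated measures to compare pre- and post-intervention", and "An alpha value of 0.05 will be used for statistical significance". Section 5a plans 20 subjects, 10 per group.

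Under CSF flow, the same section says "The velocity waveform will be averaged over the highly correlated ROI pixels", and then "The maximum and minimum peak values of the averaged CSF flow velocities will then be used for analysis". The averaging described is therefore over pixels, not over breaths or heartbeats. The waveform has two components: "The respiration frequency band and the cardiac frequency band will be defined based on the two main distinct peak amplitudes".

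Sections 2 and 4 hypothesise that training will "enable participants to sustain slow and rhythmical breathing patterns and create larger modulations in their CSF dynamics". Sections 4 and 6 say that the control arm also practises slow breathing.

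The protocol does not give the run length per breathing condition, the number of peaks per run, or whether a peak is counted per breath or per heartbeat. It also does not say whether baseline means the natural-breathing run of the same scan or the pre-intervention visit.

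**The concern.** A maximum and a mean are different statistics. The largest of several noisy peaks exceeds their average by an amount that grows with the number of peaks and with their scatter. A reader could take a ratio of 1.3 as a 30% rise over natural breathing when nothing has happened.

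The more serious worry is that the offset might move with treatment. If training makes breathing slower, a run of fixed length holds fewer breaths. If it also makes peak heights more even, the scatter falls. Either would lower the expected maximum while the typical peak stays the same, and so pull against the hypothesis of larger modulations. A single extreme is also exposed to one cough or movement, and it is noisier than a mean, which matters with 10 subjects per arm.

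**Working it through.** The protocol gives no expected ratio, SD or effect size, so there is no stated figure to reproduce. The inputs below are assumptions: independent, normally distributed peak heights, the same mean in both runs, CV of 5% to 30%, and 3 to 60 peaks per run.

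**1. Offset with no effect.** For k peaks, expected maximum ÷ mean = 1 + CV × e(k), where e(k) is the expected maximum of k standard normals: e(6) = 1.27, e(12) = 1.63, e(60) = 2.32. With k = 12 and CV 20%, 1 + 0.20 × 1.63 = 1.33. Simulation of 100,000 pairs of runs with 12 peaks each gives 1.08, 1.16, 1.33 and 1.50 at CV 5%, 10%, 20% and 30%. The offset is real.

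**2. Whether it reaches the planned test.** Write the expected ratio as approximately θ × (1 + CV × e(k)), where θ is the true practice-to-natural ratio of mean peaks. Post divided by pre is then (θ post ÷ θ pre) × (1 + CV post × e(k post)) ÷ (1 + CV pre × e(k pre)). If peak count and scatter are the same at both visits, the last factor is 1. With no change in θ, the expected pre-to-post change is zero on the raw scale too. If the denominator came only from the pre-intervention visit, both ratios would share it and the offset would still drop out of the change.

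**3. Slower breathing.** With one peak per breath and a fixed run length, going from 12 to 6 practice peaks gives:

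| CV | 12 peaks | 6 peaks | Change |
|---|---|---|---|
| 5% | 1.082 | 1.063 | −1.8% |
| 10% | 1.164 | 1.128 | −3.1% |
| 20% | 1.331 | 1.258 | −5.5% |
| 30% | 1.501 | 1.391 | −7.3% |

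If the number of breaths is fixed instead, there is no fall. The protocol's waveform also has a cardiac component. A 60-second model was therefore run with a cardiac part (65/min, amplitude 1, CV 10%) and a respiratory part (amplitude 0.5, CV 20%), both held constant. Slowing from 15 to 6 breaths per minute takes the planned ratio from 1.706 to 1.695 over heartbeat peaks (−0.6%), or from 1.163 to 1.155 over breath peaks (−0.7%). At 3 per minute the values are 1.683 and 1.148 (−1.3% each).

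**4. Noise.** A ratio is best judged by its SD relative to its own mean. At CV 20% and 12 peaks, the planned ratio has 0.139 ÷ 1.331 = 0.104 and mean over mean has 0.082 ÷ 1.004 = 0.082, so the penalty is about 1.3 times. The absolute SDs give 0.139 ÷ 0.082 = 1.7, which overstates it. With 60 peaks, (0.099 ÷ 1.465) ÷ (0.037 ÷ 1.001) is about 1.8. With serial correlation of 0.5 between peaks the penalty is 1.0 to 1.1. Maximum over maximum, which is also like for like, is noisier than the planned ratio: 0.121 against 0.104. All of this is within-session noise, and between-subject variation would dilute the difference.

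**5. The replacement.** In the mixed waveform, mean over mean counted per heartbeat stays at about 1.00 when respiratory amplitude doubles, because the respiratory wave averages out over the heartbeats. The planned ratio rises by about 34%. Ignoring scatter, the peak goes from 1 + 0.5 to 1 + 1.0, and 2.0 ÷ 1.5 = 1.33. Counted per breath, mean over mean does respond to amplitude, but with amplitudes unchanged it drifts up to 1.05 at 6 breaths per minute and 1.08 at 3.

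**The case for a change.** The strongest argument for a change is that the intervention targets the very quantities that set the offset, so it need not cancel. Scatter is the better route, since it needs no change in breath count. If the practice-run CV fell from 20% to 10% with 12 peaks and an unchanged mean peak, the planned ratio would fall from 1.33 to 1.17 (1.17 ÷ 1.33 = 0.88, or −12%), while mean over mean stayed at 1.00. In a separately built mixed waveform, halving the respiratory CV moved it only from 1.65 to 1.61 (−2.4%); cutting both CVs to 5% gave 1.53 (−7%).

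The arithmetic stands, but its premise is not in the protocol. The hypothesis of rhythmical breathing concerns timing, which is measured separately through respiration intervals; nothing predicts more even CSF peak heights. The second scan repeats the procedures of the first, and both arms train slow breathing. A bias between arms would therefore also need the arms to differ in in-scanner breathing rate or peak scatter.

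The artefact point also stands in part. With 12 peaks and CV 10%, inflating one peak by 50% takes the planned ratio from 1.16 to 1.50, and mean over mean only from 1.00 to 1.04. Averaging over pixels would not remove a cough. However, section 8 provides for technical notes on quality problems and for checking each data set after acquisition, and an isolated spike is the kind of fault such a check can catch.

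**Conclusion.** The plan can stay as it is. The ratio's level should not be read as a percentage gain over natural breathing, since its value with no effect is about 1.08 to 1.50 under the assumed CVs and 12 peaks. The planned inference concerns change between visits, where a stable offset cancels.

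Shrinkage with slower breathing reaches 2% to 7% only with fixed-length runs and one peak per breath; with heartbeat peaks present it is about 1% or less at 6 breaths per minute. Where it occurs, it works against the hypothesis rather than for it. The noise penalty against mean over mean is modest at 12 peaks and close to nil with serially correlated peaks.

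Choosing between the two ratios is a fair trade-off. The greatest velocity reached in practice, relative to typical natural breathing, is a coherent target and responds to respiratory amplitude. A heartbeat-based mean ratio hardly responds to it, and a breath-based one drifts towards the hypothesis as breathing slows. The unstated details (peak unit, run length, baseline run) are ones that analysts would fix once and apply alike to both visits and both arms. A marked fall in peak-height scatter with training would weaken this conclusion, but the protocol neither predicts nor quantifies one.
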